We will conduct a rigorous 12-week randomized controlled trial in which 160 women with overactive bladder (OAB) syndrome will be assigned to: 1) use a standard guided-breathing device to slow their respiratory rate to 5 to 10 BPM for at least 15 minutes per day at home, or 2) use an identical-appearing control device that does not guide their breathing but plays relaxing, non-rhythmic music while monitoring their spontaneous breathing pattern. Our aims are:

Aim 1: To determine whether a device-guided slow-breathing exercise program can reduce the frequency and severity of OAB symptoms in women.

Compared to controls, we hypothesize that women randomized to practice slow breathing for at least 15 minutes per day for 12 weeks will report a more than 20% greater reduction in frequency of any voiding or incontinence episodes associated with moderate or severe urgency (measured by a validated voiding diary), in addition to greater improvements in frequency of other OAB symptoms and quality-of-life impact of OAB symptoms (measured by diary or by questionnaire).

Aim 2: To determine whether this slow-breathing intervention can improve autonomic nervous system control in women with OAB, and explore change in autonomic control as a mechanism of treatment effects on OAB symptoms.

Compared to controls, we hypothesize that women randomized to practice slow-breathing will demonstrate significantly improved autonomic control as measured by high-frequency heart rate variability and pre-ejection period parameters, and that treatment effects on OAB symptoms will be at least partly mediated by improvements in autonomic control.

Aim 3: To determine whether this slow-breathing intervention can improve anxiety-related symptoms in women with OAB, and explore changes in anxiety as a mediator of treatment effects on OAB symptoms.

Compared to controls, we hypothesize that women with OAB randomized to practice slow-breathing exercises will report significant improvement in anxiety-related symptoms (as measured by validated questionnaires), and that treatment effects on OAB symptoms will be at least partly mediated by improvement in anxiety.

C. BACKGROUND & JUSTIFICATION

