Nearly one in five adult women suffer from overactive bladder, a syndrome characterized by recurrent, strong urges to void, increased frequency of daytime or nocturnal voiding, and in many cases involuntary leakage of urine when women are unable to get to the toilet in time.¹⁻³ Among women in the community, OAB is associated with sleep disruption, social isolation, decreased work productivity, sexual dysfunction, and depression.²⁻⁹ When further complicated by involuntary urine leakage (i.e., urgency incontinence), OAB can also lead to falls and fractures, increased caregiver burden, and loss of ability to live independently, with potentially devastating consequences for quality of life.¹⁰⁻¹²

Currently, the most widely used treatments for OAB are anticholinergic drugs that can decrease involuntary bladder contractions, but are associated with multiple problematic side effects such as dry mouth, constipation, and even cognitive impairment, especially in older women.¹³⁻¹⁷ As a result, many clinicians are

reluctant to prescribe these drugs to older women, and at least half of women who start anticholinergic drugs for OAB discontinue them in less than a year.¹⁸ While behavioral treatments such as pelvic floor exercises can be effective in reducing OAB, these are only modestly effective in the absence of time-intensive, one-on-one training with physical therapists.^{19,20} *At this time, there is an urgent need for alternate therapies for OAB that are more effective, better tolerated, and more widely generalizable.*

Recent clinical studies have documented strong associations between self-reported anxiety, perceived stress, and OAB, including an increased risk of new-onset OAB in women with high baseline anxiety.²¹⁻²⁴ Prior research has also shown that many women with OAB have impaired autonomic nervous system control as documented by heart rate variability measures²⁵⁻²⁸ that are in turn associated with clinical anxiety disorders. These findings suggest that OAB symptoms, anxiety disorders, and autonomic dysfunction may share important underlying physiologic mechanisms. *As a result, behavioral treatment approaches that decrease anxiety and improve autonomic control may offer a novel way to alleviate OAB symptoms without exposing women to the side effects of anticholinergic drugs.*

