To complement subjective data on sleep quality assessed by questionnaire, actigraphy data will be collected over a 3-day period prior to the Baseline and 12 Week visits using the Motion Logger actigraph (Ambulatory Monitoring, Inc., Ardsley, NY), a small device that designed to be worn on the wrist. This wrist actigraph contains a piezoelectric linear accelerometer (sensitive to 0.003 g and above), a microprocessor, 32K RAM memory, and associated circuitry. The orientation and sensitivity of the accelerometer are optimized for highly effective sleep-wake inference from wrist activity.^{54,55} The Motion Logger is able to collect data in three modes simultaneously: the zero-crossing mode, which has been rigorously validated for sleep-wake activity,⁵⁴ time-above-threshold, and digital integration mode. The output from the actigraph supplies information about total sleep time, percent sleep, number and duration of awakenings per night, and circadian rhythms.

D.5.6 Demographic and clinical covariates

Structured-item questionnaires will collect data on the following covariates at screening/baseline to provide information on eligibility, characterize the study cohort, provide evidence that treatment groups were comparable at baseline, and guide statistical adjustments in the unlikely situation that groups are not balanced at baseline: demographics (date of birth, race/ethnicity, education, relationship/marital status), urologic history (age of onset of OAB, past urologic surgery, prior treatment of OAB, past response to treatment for OAB), current medications (including psychoactive drugs), gynecologic history (gravidity, parity, menopausal history, hysterectomy, oophorectomy), health-related habits (tobacco and alcohol use, physical activity), and selected co-morbid chronic health conditions (such as diabetes). Height, weight, and seated resting blood pressure, heart rate, and respiratory rate will also be measured at visits. Women will undergo urinalysis testing at baseline to assess for urinary tract infection or hematuria, and to rule out pregnancy.

D.5.7 Safety measures

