The primary outcome will be change in the frequency of any voiding or incontinence episodes associated with at least moderate urgency (measured over 3 days using the validated voiding diary and urgency scale²⁹⁻³¹) from baseline to 12 weeks. Treatment effects will be estimated using ANCOVA models, adjusting for baseline frequency of the outcome. Analyses will be by intention to treat, according to treatment assignment, and without regard to adherence with use of the active or control interventions. For additional confirmation of treatment effects on this primary outcome, we will also use ANCOVA models to examine treatment effects on frequency of other OAB symptoms, including 1) urgency incontinence, 2) voiding or incontinence episodes associated with a *severe* sensation of urgency, 3) total daytime and nighttime voiding (regardless of whether they are associated with urgency), and 4) Overactive Bladder Symptom Composite Scores, as well as on scores on validated urinary symptom bother and impact questionnaires (i.e., the OAB-Q, USIQ, UDI-6, PPBC, and PSQI). Outcomes will be transformed if Shapiro-Wilk tests for normality of the residuals from initial models are significant at $p < 0.01$. In secondary analyses, if treatment benefits are detected at 12 weeks, we will also assess for persistence of effects 12 weeks post-treatment using data from the 24-week mail-in diary and questionnaires, and assess for dose response in treatment effects based on duration and cumulative time of treatment exposure (see the “Additional statistical issues” section below).

Aim 2: To determine whether this slow-breathing intervention can improve autonomic nervous system control in women with OAB, and explore change in autonomic control as a mechanism of treatment effects on OAB symptoms.

Expected outcomes: Women randomized to practice slow-breathing will demonstrate significantly improved autonomic control as measured by high-frequency heart rate variability and pre-ejection period parameters, and that treatment effects on OAB symptoms will be at least partly mediated by improvements in autonomic control.

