Secondary outcomes include 12-week change in autonomic control as assessed by high frequency heart rate variability (RSA) and pre-ejection period (PEP), as the purest available measures of parasympathetic and sympathetic function. Treatment effects on each of these measures will initially be estimated using ANCOVA models, first to examine effects on resting parameters, followed by examination of effects on rest-to-stress change (i.e., reactivity) while adjusting for baseline levels of each parameter. Treatment effects will again be examined by intention to treat, according to treatment assignment, and without regard to adherence. Autonomic parameters will be transformed as necessary if their distributions appear significantly skewed. We will then assess for mediation of treatment effects on OAB symptoms by improvement in autonomic control using structural equation modeling. This will involve fitting an initial model that includes both autonomic parameters and anxiety symptoms (as described below in the statistical plan for Aim 2), then extracting coefficients for each of the hypothesized mediating pathways.

Aim 3: To determine whether this slow-breathing intervention can improve anxiety-related symptoms in women with OAB, and explore changes in anxiety as a mediator of treatment effects on OAB symptoms.

Expected outcomes: Women with OAB randomized to practice slow-breathing exercises will report significant improvement in anxiety-related symptoms (as measured by validated questionnaires), and treatment effects on OAB symptoms will be at least partly mediated by improvement in anxiety.

Additional outcomes will include change in anxiety symptoms from baseline to 12 weeks, measured by scores on the validated STAI, HADS, PSS, and BDI questionnaires. Intervention effects will again be estimated using ANCOVA, adjusted for baseline questionnaire scores. Anxiety symptom outcomes will be transformed as necessary if their distributions appear skewed. To assess for mediation of treatment effects on the primary outcome by change in anxiety symptom scores (as well as autonomic parameters as noted in the statistical plan for Aim 2), we will use structural equation modeling as outlined above).

D.10.2 Sample size estimates

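### The mediation model for Aims 2 and 3 has no protection against mediator–outcome confounding, so it can show mediation where none exists

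*Combined protocol and SAP*

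**What the plan says.** The Aim 2 analysis in D.10.1 states: "We will then assess for mediation of treatment effects on OAB symptoms by improvement in autonomic control using structural equation modeling". One model is to hold both the autonomic parameters and the anxiety measures, and mediation is read off by "then extracting coefficients for each of the hypothesized mediating pathways". Aim 3 uses the same model for "mediation of treatment effects on the primary outcome by change in anxiety symptom scores".

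The model is not specified further. The Aim 2 text refers the reader to a description in the Aim 2 plan, which is where that sentence already stands, and Aim 3 refers back. No baseline terms, confounders, identifying assumption or sensitivity analysis are listed for it. The covariates in D.5.6 have one stated use in adjustment, to "guide statistical adjustments in the unlikely situation that groups are not balanced at baseline", which concerns the arms and not the mediator–outcome relation.

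On status, the aim is worded as to "explore change in autonomic control as a mechanism of treatment effects on OAB symptoms", but the hypothesis in section B and the expected outcome in D.10.1 is that "treatment effects on OAB symptoms will be at least partly mediated by improvements in autonomic control".

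**The concern.** An indirect effect is the product of two paths. Random allocation identifies the effect of treatment on the mediator. It does not identify the effect of the mediator on OAB symptoms, because women were not randomised to levels of anxiety or autonomic tone. Anything that drives both will appear in that second coefficient.

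The rationale in section C names a candidate: it suggests that "OAB symptoms, anxiety disorders, and autonomic dysfunction may share important underlying physiologic mechanisms". A shared mechanism is a possible common cause of mediator and outcome. It would bias the second path whichever visit supplied the mediator, so it is separate from the question of time order. Heart rate variability and pre-ejection period are measured only at baseline and 12 weeks.

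At stake is what Aims 2 and 3 may conclude. If treatment improves a mediator and the shared state fluctuates over the trial, the model would attribute part of the treatment effect to a pathway that does not operate. The primary treatment comparison is unaffected.

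**Working it through.** **The plan's own figures.** D.10.2 gives no figure for mediation. Its primary calculation can be followed: cross-sectional SD = 5.8/√(2 × (1 − 0.59)) = 6.41; residual SD = 6.41 × √(1 − 0.59²) = 5.17. With 68 completers per arm (80 less 15%), the detectable difference at 80% power is 2.80 × 5.17 × √(2/68) = 2.48 episodes, or 20.7% of 12, which fits the stated figure of more than 20%. For secondary outcomes, unadjusted, 2.80 × √(2/68) = 0.48 SD, which fits the stated 0.5 SD.

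**Inputs.** From the documents: 136 completers; 0.5 SD as the detectable effect on anxiety and autonomic measures; within-subject correlation w = 0.6, the middle of the stated 0.4 to 0.8. Assumptions: true mediator shift a = 0.5 SD; share s of each variable's variance due to the shared cause, 0.2 to 0.4; 12-week correlation k of the shared cause (its stability), 0.6, 0.8 or 1; one mediator; **no true mediator-to-OAB effect**; scales oriented so that improvement has the same sign.

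**Residual mediator–outcome correlation r, given treatment.**
- Change scores: r = s(1 − k)/(1 − w), and the SD of change is √(2(1 − w)).
- Both baselines as covariates: with L₁ = 1 + s − (w + ks)²/(1 + s) and L₂ = 1 − s − (w − ks)²/(1 − s), r = (L₁ − L₂)/(L₁ + L₂), and the residual SD is √((L₁ + L₂)/2).

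**Rate of declaring mediation** (both paths significant, two-sided 5%), approximately P_a × P_b:
- P_a = Φ((a/SD)√(n/4) − 1.96)
- P_b = Φ(atanh(r)√(n − 4) − 1.96), plus the negligible other tail. When r = 0, P_b is 0.05.

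Example, s = 0.2, k = 0.6, change scores: r = 0.2 × 0.4/0.4 = 0.20; a/SD = 0.5/0.894 = 0.559; P_a = Φ(3.26 − 1.96) = 0.903; P_b = Φ(2.33 − 1.96) = 0.644; product 0.58.

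| Stability k | Change scores, s = 0.2 / 0.3 / 0.4 | Both baselines, s = 0.2 / 0.3 / 0.4 |
|---|---|---|
| 0.6 | 58% / 85% / 90% | 61% / 90% / 95% |
| 0.8 | 19% / 37% / 58% | 29% / 57% / 82% |
| 1 (stable) | 5% / 5% / 5% | 9% / 16% / 29% |

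Simulation agrees: 60–90% and 61–95% at k = 0.6; 20–60% and 30–82% at k = 0.8; 4% and 10–30% at k = 1. A separate simulation at k = 0.6 gave 56–89% and 59–96%. If 0.6 is instead the stability of only the unshared part of each variable, the k = 0.8 row becomes 23–80% and 32–90%.

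**Size of the false pathway.** With a total effect of 0.4 SD on OAB (assumed; the plan's 20% is 2.4/6.41 = 0.37 SD), the share called mediated is 0.5r/0.4. At k = 0.6 that is 25%, 38% and 50%.

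**What lowers the rate.**
- No effect on the mediator: P_a = 0.05, so the rate cannot exceed about 5%.
- a = 0.3 SD, change scores, k = 0.6: P_a = 0.50, and the rate is 32% to 50%.
- Autonomic measures come from one site; the number of women is not given. At an assumed n = 68, k = 0.6, change scores, the formula gives 23% to 59% and simulation 23% to 54%.
- Four mediators in one model (n = 136, k = 0.6, s = 0.2 and 0.4, change scores or both baselines): a given pathway is falsely flagged in 30% to 52% of simulated trials, and at least one pathway in 75% to 97%.

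**The case against.** The strongest reply has four parts.

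1. **Status.** The aims say mediation will be explored, and no primary conclusion depends on it. That lowers the priority. It does not settle the matter, because the expected outcomes state mediation as a hypothesis and a biased coefficient is no less biased for being exploratory.

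2. **Change scores.** The anxiety mediator is described as a change, and the primary and autonomic outcomes are 12-week changes. Change scores remove a fully stable shared cause (about 5% in the table). This stands, and section C does not say that the shared mechanism drifts over 12 weeks. But the plan does not commit the model to change scores, and they do not protect if the shared state moves.

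3. **Assumed inputs.** The 0.5 SD shift appears in D.10.2 only as a detectable difference, and the documents give no shared-cause variance or stability. This stands. The high rates are conditional.

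4. **Sample and model.** The single-site sample lowers the rates for heart rate variability and pre-ejection period, and the joint model lowers the rate for any one pathway. Both points stand, although with several mediators the chance of at least one false pathway remains high.

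**Conclusion.** The gap is real. D.10.1 reads path coefficients as mediation, only one of the two paths is randomised, section C offers a reason to expect confounding of the other, and the plan neither states nor examines the assumption of no such confounding.

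The size is conditional. With a 0.5 SD mediator shift, shared-cause variance 0.2 to 0.4, 136 women and one mediator, false mediation occurs in about 55% to 95% of trials at stability 0.6 and about 20% to 80% at stability 0.8. It is lower for the single-site autonomic measures. It is about 5% if treatment does not move the mediator, and about 5% with change scores if the shared cause is stable.

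A reader might infer that the planned analysis would usually find mediation where there is none. The documents do not support that. Section C speaks of mechanisms that may be shared, and the rate passes one half only with a sizeable mediator shift and a changing shared cause, neither of which the documents give as an expected value. The supported statement is that the plan cannot distinguish mediation from a shared changing state, and that the error would be frequent if treatment shifts the mediator by about 0.5 SD and that state does change.

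**What to change.** In D.10.1, Aims 2 and 3:

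- Report each indirect effect as a function of the mediator–outcome residual correlation over a prespecified range, with the value at which the estimate, and its confidence limit, reaches zero. In the one-mediator model the estimate reaches zero when the assumed correlation equals the observed residual correlation r. The lower limit of the mediator–outcome path reaches zero at about tanh(atanh(r) − 1.96/√(n − 4)). For r = 0.30 that is 0.14 with 136 women and 0.06 with 68.
- State the assumption of no unmeasured mediator–outcome confounding, and describe a positive finding as consistent with mediation under that assumption, not as an established mechanism.
- Specify the model, and fit it both with change scores and with baseline mediator and baseline outcome as covariates. Neither form is better throughout: at s = 0.4 the false rates are 5% against 29% when the shared cause is stable, but 90% against 95% at stability 0.6, and with real effects the two forms use the data differently.

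Do not make the claim depend on the interval excluding zero for every residual correlation up to the baseline mediator–outcome correlation. That correlation contains any true causal effect. In simulations of genuine full mediation without confounding (path 0.2 to 0.5, 136 women, 0.5 SD shift), such a rule cut power from 57–95% to about 5–8%.

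The cost is SAP wording and reruns of the same model with a fixed correlation. No new data are needed and the primary analysis does not change. The downside is a little more analysis and a more cautious statement about mechanism.

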Like participants in the active group, participants in the control group will be asked to use their devices for at least 15 minutes per day for 12 weeks. Participants in the control group will be given the same instructions as those randomized to use the active RESPeRATE device, except that they will be told to simply listen to the music played by the device rather than using the device as a guide for breathing. Like the active device, the control device will automatically collect data on: a) time, date, and number of sessions in which it was used; b) duration of time for each session; c) average and range of respiratory rate, and d) data quality (i.e., percent time that breathing was detected by the sensor).

This control device will control for the fact that participants will be sitting still and relaxing while wearing the RESPeRATE device breathing sensor belt for at least 15 minutes per day. It will also allow collection of data on spontaneous breathing pattern in the control group and monitoring of adherence to use of the control intervention.

D.4.4 Randomization

Randomization to either the active or control device will be performed by computer at a 1:1 ratio, using randomly permuted blocks of 2, 4, and 6. Following a brief run-in period in which women use the control device and complete other eligibility assessment procedures, women will be randomized either to: 1) receive a new active RESPeRATE device that paces respiration at a slow rate, or 2) continue using a control device that monitors spontaneous breathing rate while playing non-rhythmic music. Sealed, opaque envelopes will be prepared by the study statistician containing treatment assignment codes. When a participant fulfills study inclusion and exclusion criteria, the next sequential envelope will be opened by study staff and treatment assignment will be irrevocably entered on a participant case report form. A subset of the randomization envelopes will be assigned to the Oakland Satellite office.

D.4.5 Blinding

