- A. Heart rate variability: Heart rate variability (i.e., fluctuation in instantaneous heart rate that results from autonomic influences on the sinus node) is a well-established measure of overall autonomic balance, and a validated marker of risk for adverse outcomes of other chronic conditions associated with autonomic dysfunction such as coronary disease and heart failure⁴¹. In particular, the high frequency (0.12-0.40 Hz) component of heart rate variability provides a reliable marker of *parasympathetic* autonomic activity, based on autonomic blockade studies showing that heart rate variability in the high frequency range is influenced by vagal but not sympathetic influences on the heart⁴²⁻⁴⁴. Measurements will be obtained at baseline and 12 weeks for visits at the [name] site only using a Biopac MP150 monitoring system (Santa Barbara, CA), according to protocols established by the North American Society of Pacing and Electrophysiology⁴⁵. Specifically, two electrocardiograph (ECG) electrodes will be attached to participants' torso/chest, and a 20-minute continuous ECG recording will then be taken with the participant in the seated position. Prior to measurement, women will be queried about any history of cardiac arrhythmias that could influence heart rate variability interpretation. To minimize diurnal variation, recordings will be obtained in the same 2-hour time of day at both visits. Women will sit in a quiet, ambient-temperature room, and will also be asked to abstain from tobacco or alcohol for 24 hours prior to recording. For 10 minutes during recording, they will also be asked to perform two computer-based stress tasks designed to assess vagal reactivity and sympathetic nervous system activity. Data will be analyzed using Mindware software (Gahanna, OH), which will calculate multiple time domain heart rate variability parameters (e.g., mean heart rate, standard deviation of N-N interval, square root of mean squared difference of successive N-N

intervals), as well as frequency domain heart rate variability parameters reflecting the distribution of heart rate variability over different frequencies (e.g., high frequency (0.12-0.40 Hz), low frequency (0.04-0.12 Hz), and low frequency/high frequency ratio).

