- B. Pre-ejection period: Pre-ejection period (i.e., PEP, or, the time period during which the left ventricle of the heart contracts while the aortic and mitral valves are still closed) is an established measure of *sympathetic* autonomic activity that can be measured non-invasively using impedance cardiography^{42,44}. Using the same Biopac MP150 monitoring system used to assess heart rate variability (see above), cardiac impedance measurements will be obtained at baseline and at 12 weeks for visits at the [name] site only. According to established protocols⁴⁶, a standard tetrapolar electrode system will be attached to each participant while in the seated position (two inner electrodes placed at the xiphisternal joint and the base of the neck, outer electrodes place 3 cm distally to the inner electrodes). Impedance cardiogram recordings will be obtained by the Biopac monitor at the same time that heart rate variability recordings. Prior to measurement, women will be queried about any history of heart murmurs suggesting heart valve abnormalities that could influence pre-ejection period interpretation. Cardiac PEP will be determined by calculating the time between ventricular depolarization (assessed by ECG output) and the B point of the dZ/dt wave (measured by impedance cardiography). Standard Mindware software will be used to generate the dZ/dt waveform by averaging minute-to-minute ECG and impedance data for each subject.

D.5.3. Anxiety and perceived stress (assessed at baseline, 6 week, 12 weeks, and 24-week mail-in)

Validated self-administered questionnaires will be used to gather additional information about somatic and cognitive anxiety, depression, and perceived stress.

- A. Somatic anxiety: Somatic anxiety (i.e., the affective component of anxiety believed to be related to autonomic physiological arousal response) will be measured using the trait component of the Spielberger State Trait Anxiety Inventory (STAI), a 20-item self-administered measure validated in both clinical and psychiatric populations, including patients with bladder symptoms.^{47,48} Scores range from 20 to 80, with higher scores indicating greater somatic anxiety.

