Sample size is calculated based on parameter estimates derived from prior trials conducted by the investigators, such as BRIDGES and PRIDE:^{64,65} a) mean baseline frequency of urgency- associated voiding or incontinence episodes of 12; b) mean reduction in frequency in controls of 30%; c) standard deviation (SD) of change in urgency-associated voiding or incontinence frequency of 5.8 and d) correlation between baseline and follow-up values of 0.59. We assume that a clinically significant effect in the primary outcome would be a net reduction in the active group of more than 20% than that of controls. Under these assumptions, a sample size of 160 (80 per group) would provide 80% power in 2-sided tests with type-I error of 5% to detect between-group differences of >20% in the active vs. control arm. This accounts for reduction in the residual variance achieved by adjustment for baseline frequency, as well as loss to follow-up of 15%. In comparisons of changes in secondary outcomes (other OAB symptoms, impact scores, anxiety, and autonomic parameters), the sample will provide 80% power in 2-sided tests with type-I error of 5% to detect differences of 0.5 SDs, depending on within-subject correlation of outcomes, assumed to fall in the range of 0.4 to 0.8.

D.10.3 Drop-out rates

Given that the proposed trial is of short duration, dropout levels are expected to be low (i.e., less than 15%). The assumption of non-informative dropout will be examined by comparing baseline and early post-randomization characteristics of dropouts and non-dropouts. If dropout is differential between groups, analyses will be adjusted for maldistributed variables. In a sensitivity analysis, we will also use multiple imputation of missing outcomes, in conjunction with standard methods for calculating summary estimates, confidence intervals, and p-values.⁶⁶

D.10.4 Dose effects

In the event that treatment appears effective in improving OAB symptoms over 12 weeks, we will use a closed test procedure to assess for a dose response in duration of treatment without inflating type-I error:⁶⁷ specifically, if we detect a statistically significant benefit over 12 weeks at an alpha of 0.05, we will then assess change from baseline to 6 weeks, and from 6 to 12 weeks, also at alpha of 0.05. In exploratory

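### The 80% power stated for the autonomic outcomes is worked on the whole sample, but heart rate variability and pre-ejection period are measured at only one of two sites

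*Combined protocol and SAP*

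**What the plan says.** Section D.10.2 sets the sample at 160 women, 80 per group, allows for 15% loss to follow-up, and then makes one power statement for all secondary outcomes. It opens "In comparisons of changes in secondary outcomes (other OAB symptoms, impact scores, anxiety, and autonomic parameters" and continues that "the sample will provide 80% power in 2-sided tests with type-I error of 5% to detect differences of 0.5 SDs". The plan takes the correlation between a woman's repeated values to lie between 0.4 and 0.8. No separate number is given for any of these outcomes.

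Section D.5.2 A says of HRV: "Measurements will be obtained at baseline and 12 weeks for visits at the [name] site only". Section D.5.2 B says of PEP: "cardiac impedance measurements will be obtained at baseline and at 12 weeks for visits at the [name] site only". The site name is removed, but the restriction to a single site is legible.

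A second site takes part in randomisation. Section D.4.4 states: "A subset of the randomization envelopes will be assigned to the Oakland Satellite office". Section D.4.5 refers to diaries from two sites, and section D.6 describes visits at two locations.

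Section D.6.4 (baseline visit), section D.6.8 (12-week visit) and the schedule in Appendix A list HRV and impedance cardiography with no site limit.

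**The concern.** The power statement and the measurement plan use different denominators. Every woman randomised at the other site lacks HRV and PEP by design, so the number available for Aim 2 is below the 68 per arm on which the statement rests. Section D.8.2 also lets women with adhesive sensitivity decline these measurements, which can only lower the number further.

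Aim 2 is one of three specific aims. Its treatment comparisons, and the autonomic part of the mediation model in section D.10.1, depend entirely on this subset. If the statement is left as it is, a null result for HRV or PEP could be presented as coming from a comparison with 80% power at 0.5 SD when nobody has worked out whether that is so.

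**Working it through.** **Inputs from the documents.** Two-sided alpha 0.05; target power 80%; difference 0.5 SD; 80 randomised per arm; 15% loss; correlation r between baseline and follow-up of 0.4 to 0.8 (all D.10.2); ANCOVA adjusted for baseline (D.10.1, Aim 2).

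**Assumptions.** The share of completers at the measuring site is not given, so it is varied. Loss is taken as 15% at both sites, arms as equal within site, and refusals as zero. D.10.2 does not say whether 0.5 SD means the SD of the outcome or the SD of change, so both are shown.

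**Step 1: the plan's own figure.** Completers per arm: 80 × 0.85 = 68. For an unadjusted comparison the noncentrality is 0.5 × √(68/2) = 2.915, which gives 83% power (82.5% by noncentral t). The detectable difference is (1.960 + 0.842) × √(2/68) = 0.48 SD, which rounds to 0.5. For the whole sample the statement is sound as a rounded floor.

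**Step 2: ANCOVA.** In units of the outcome SD, the residual SD is √(1 − r²): 0.917 at r = 0.4 and 0.600 at r = 0.8. With equal variances at the two times, the SD of change is √(2(1 − r)) outcome SDs, so in units of the SD of change the residual SD is √[(1 − r²)/(2(1 − r))] = √((1 + r)/2): 0.837 at r = 0.4 and 0.949 at r = 0.8. Power comes from the noncentral t with noncentrality (0.5/residual SD) × √(n/2) and 2n − 3 degrees of freedom.

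Completers per arm needed for 80% power:

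| r | 0.5 outcome SD | 0.5 SD of change |
|---|---|---|
| 0.4 | 54 | 45 |
| 0.5 | 49 | 49 |
| 0.6 | 42 | 52 |
| 0.7 | 34 | 55 |
| 0.8 | 24 | 58 |

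The worst cases are 54/68 = 79% and 58/68 = 85%. The claim therefore begins to fail at one end of the plan's correlation range once the other site supplies more than about 21% (outcome SD) or 15% (SD of change) of completers.

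**Step 3: power by share measured.**

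| Share at measuring site (assumed) | n per arm | Outcome SD, r = 0.4 to 0.8 | SD of change, r = 0.4 to 0.8 |
|---|---|---|---|
| 100% | 68 | 88.5% to 99.8% | 93% to 86% |
| 85% | 57.8 | 83% to 99% | 89% to 80% |
| 75% | 51 | 78% to 99% | 85% to 75% |
| 50% | 34 | 60% to 92% | 68% to 57% |

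Worked example: 34 per arm, r = 0.4, outcome SD. Noncentrality = (0.5/0.917) × √17 = 2.25 on 65 degrees of freedom; power is 60%. In the same units power is 72% at r = 0.6, 81% at 0.7 and 92% at 0.8. The difference detectable with 80% power at r = 0.4 is about 2.80 × 0.917 × √(2/34) = 0.62, or 0.63 outcome SD by noncentral t.

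**Step 4: arm balance within the measuring site.** Section D.4.4 names no stratification factor. The least favourable case was simulated: one list in blocks of 2, 4 and 6, with site independent of block and 50% or 75% of women at the measuring site. The median difference between arms was 4 women and the 95th percentile 11 to 12. Mean power loss was under 0.3 points, and about 1 point at the 95th percentile.

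**The case against.** The strongest reply is that no shortfall has been shown. The second location is called a satellite, receives only part of the envelopes, and works from a rented office to which equipment is brought. That suggests, without proving, that it is the smaller site. If it supplies 15% or less of completers, the 80% figure survives at every correlation and in both SD units. The plan also says that power depends on the correlation, and at 0.7 or 0.8 in outcome-SD units even half the sample is enough. All of this stands, and it is why the result is given as a range.

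Three stronger readings are tempting, and the documents do not support them.

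- A reader might infer that Aim 2 is underpowered. That needs a site split the documents do not give.
- A reader might infer an arithmetic error in D.10.2. The whole-sample figure reproduces as a slightly conservative floor; the fault lies in applying it to a subset.
- A reader might infer that unstratified randomisation harms the Aim 2 comparison, or that site differences add noise to the primary analysis. Section D.4.4 does not say whether the satellite's envelopes are a separate list, whole blocks or a run of one list. A contiguous run would leave the arms nearly balanced: in simulation the median difference was 1 woman and the 95th percentile 3. Even the least favourable case costs about 1 point of power. No between-site variance is given, so the second half of that inference has no figure behind it.

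What the reply does not remove is the mismatch itself: the stated power uses a number of women that HRV and PEP will not have.

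**Conclusion.** The point holds as a mismatch between the power statement and the measurement plan. The 80% at 0.5 SD in D.10.2 is not supported for HRV and PEP, because it rests on 68 completers per arm from both sites while these measures come from one.

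The consequence ranges from none, if about 85% or more of completers are measured, to power of 57% to 68% (SD of change) or 60% to 92% (outcome SD) if half are. These figures assume 15% loss at both sites, equal arms within site, no refusals, and the plan's own correlation range. Refusals would lower them. That the two figures disagree is certain; how far power falls cannot be settled from the documents. The correction is worth making because it is specific and nearly free, and because a whole specific aim relies on the number.

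**What to change.** In D.10.2:

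- Remove autonomic parameters from the whole-sample power statement.
- State how many women are expected to have HRV and PEP at both baseline and 12 weeks, after loss and refusals.
- Give a separate power or detectable difference for that number, with the correlation used and whether the SD is that of the outcome or of change. As an illustration only: if half the women are measured and r = 0.4, the detectable difference is 0.63 outcome SD.

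Reconcile sections D.6.4 and D.6.8 and Appendix A with D.5.2, so that the site limit appears wherever these measures are scheduled.

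The cost is a few sentences and one recalculation, with no extra participants.

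Optionally, prepare the envelopes as separate permuted-block lists for each site, say so in D.4.4, and include site in the models. This costs a second list and one degree of freedom. The expected gain is about 1 point of power or less, so it is good housekeeping and the point does not depend on it.
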